
Statistical methods at interim analysis: The Safety population included all subjects who took at least 1 dose of study drug. The Efficacy population included all enrolled subjects who had baseline and Week 52 exercise capacity data for which site-based data quality assurance process was complete at data cut-off.

Three treatment groups were defined:
 
• Udenafil-Udenafil, which included subjects who received udenafil in the FUEL and FUEL Extension studies• Placebo-Udenafil, which included subjects who received placebo in the FUEL study and udenafil in FUEL Extension• De Novo: Subjects who did not participate in the FUEL study and received udenafil in FUEL Extension

For efficacy and safety summaries, the Placebo-Udenafil and De Novo groups were combined (denoted as Placebo/De Novo-Udenafil).

All summaries were descriptive. Descriptive statistics for categorical endpoints included the number and percent of subjects in each treatment group and category. Quantitative endpoints were summarized for each treatment group with the mean, median, standard deviation, minimum value, and maximum value. Missing data were not imputed.

Baseline was defined as the last measurement before receipt of udenafil in FUEL Extension. For the Udenafil-Udenafil group, change to Week 52 of FUEL Extension measures change in exercise capacity between 26 weeks and 78 weeks of udenafil treatment. This change represents persistence of initial effectiveness beyond 26 weeks. For the Placebo-Udenafil and De Novo groups, change to Week 52 of FUEL Extension measures change in exercise capacity from pre-udenafil to following 52 weeks of udenafil treatment.

Statistical methods (continued):

For each efficacy endpoint, descriptive statistics were summarized for baseline, Week 52, and Week 52 change from baseline. A 2-sided, 95% confidence interval was calculated for change from baseline for each group.

Safety analyses were descriptive with no formal hypothesis testing. All AEs were classified by the Medical Dictionary for Regulatory Activities with respect to system organ class and preferred term. Subject incidence of all treatment-emergent adverse events (TEAEs), and TEAEs that are treatment-related, serious, serious treatment-related, and any TEAE leading to study discontinuation were tabulated. Number (%) of subjects who were hospitalized, had a cardiac transplant, or died were tabulated.

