Incidence of potentially clinically significant changes from pre dose values in blood pressure and heart rate were tabulated at i) post first study dose but before the self-limited 6-minute walk, ii) after the 6-minute walk, and iii) at any time after dosing.

SUMMARY – CONCLUSIONS

EFFICACY RESULTS:

For the Udenafil-Udenafil group, change to Week 52 of FUEL Extension measures change in exercise capacity between 26 weeks and 78 weeks of udenafil treatment. This change represents persistence of initial effectiveness beyond 26 weeks. For the Placebo/De Novo-Udenafil group, change to Week 52 of FUEL Extension measures change in exercise capacity from pre-udenafil to after 52 weeks of udenafil treatment.

In the Placebo/De Novo-Udenafil group, mean exercise capacity and myocardial performance improved between pre-udenafil and after 52 weeks of udenafil treatment:

- Mean increase at peak exercise effort in VO₂ (58.00 mL/min), work rate (5.78 watts), and minute ventilation (2.41 L/min). When VO₂ was standardized by each subject's body weight, a mean decrease was observed (-0.93 mL/kg/min; 95% CI: -1.7 to -0.2 mL/kg/min).
- Mean increase in VO₂ at VAT of 12.90 mL/min (95% confidence interval [CI]: -23.1 to 48.9 mL/min). When standardized by each subject's body weight, a mean decrease was observed (-0.93 mL/kg/min; 95% CI: -1.5 to -0.4 mL/kg/min).
- Mean decrease in VE/VCO₂ at VAT of -0.77 (95% CI: -1.4 to -0.2).
- Mean increase in work rate at VAT of 0.58 watts (95% CI: -2.6 to 3.7 watts).
- Mean decrease in MPI of -0.04 (95% CI: -0.1 to 0.0).

In the Udenafil-Udenafil group, mean exercise capacity was improved while myocardial performance did not deteriorate between 26 weeks and 78 weeks of udenafil treatment:

- Mean increase at peak exercise effort in VO₂ (38.00 mL/min), work rate (2.99 watts), and minute ventilation (2.56 L/min). When VO₂ was standardized by each subject's body weight, a mean decrease was observed (-1.45 mL/kg/min; 95% CI: -2.3 to -0.6 mL/kg/min).
- Mean increase in VO₂ at VAT of 6.57 mL/min (95% CI: -47.9 to 61.0 mL/min). When standardized by each subject's body weight, a mean decrease was observed (-1.25 mL/kg/min; 95% CI: -2.1 to -0.4 mL/kg/min).
- Mean decrease in VE/VCO₂ at VAT of -0.66 (95% CI: -1.6 to 0.3).
- Mean increase in work rate at VAT of 0.26 watts (95% CI: -5.1 to 5.6 watts).
- Negligible mean decrease in MPI of -0.0 (95% CI: 0.0 to 0.0).

SAFETY RESULTS:

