No subject died during the study. At least 1 serious TEAE was reported by 14 (10.9%) subjects in the Udenafil-Udenafil group and 24 (13.9%) subjects in the Placebo/De Novo-Udenafil group. Among the serious TEAEs reported, cardiac failure was reported by 4 subjects in the Placebo/De Novo Udenafil group, transient ischaemic attack was reported by 2 subjects in the Placebo/De Novo Udenafil group and 1 subject in the Udenafil-Udenafil group, abdominal pain and appendicitis were reported by 2 subjects each in the Udenafil-Udenafil group, protein-losing gastroenteropathy, gastroenteritis, and syncope were reported by 2 subjects each in the Placebo/De Novo Udenafil group, and anaemia, supraventricular tachycardia, ventricular tachycardia, and vomiting were reported by 1 subject each in the Udenafil-Udenafil and Placebo/De Novo Udenafil groups. All other serious TEAEs were reported by no more than a single subject in either treatment group. Hospitalization was reported for 14 (10.9%) subjects in the Udenafil-Udenafil group and for 24 (13.9%) subjects in the Placebo/De Novo Udenafil group. No transplants were reported.

At least 1 TEAE leading to temporary or permanent discontinuation of study drug was reported by 20 (15.6%) subjects in the Udenafil-Udenafil group and 22 (12.7%) subjects in the Placebo/De Novo-Udenafil group. The most common types of TEAEs that led to temporary or permanent discontinuation of study drug were associated with nervous system disorders including headache (2 Udenafil-Udenafil, 4 Placebo/De Novo-Udenafil), migraine (2 Udenafil-Udenafil, 2 Placebo/De Novo-Udenafil), and dizziness (1 Udenafil-Udenafil, 2 Placebo/De Novo-Udenafil). Dizziness was the most commonly reported TEAE of special interest (11.7% Udenafil-Udenafil and 12.7% Placebo/De Novo-Udenafil). None of the events of dizziness was serious, all were considered mild or moderate in intensity and most required no change in study drug. The other TEAEs of interest including syncope, presyncope, and hypotension occurred in <4% of subjects in either treatment group.

No clinically important findings were observed in the evaluations of vital signs.

CONCLUSION:

Improvement in exercise capacity was observed in those who were previously naïve to udenafil therapy, and there was persistence of effect on exercise capacity for those who were previously treated with udenafil. Udenafil administered orally at 87.5 mg BID for 52 weeks was safe and well tolerated in this study.

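### The FUEL Extension synopsis concludes that the exercise effect persisted to 78 weeks, but an uncontrolled, descriptive within-group change can neither show nor refute that

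*Protocol*

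**What the plan says.** Section 2 of the Protocol document is the synopsis of the open-label extension. The report body that follows, and the SAP, belong to the 26-week FUEL trial. No extension SAP or extension report body was supplied.

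The synopsis gives the extension's objectives as safety and pharmacodynamic profile, its reference therapy as none, and its summaries as descriptive. On efficacy it says:

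- Population: "The Efficacy population included all enrolled subjects who had baseline and Week 52 exercise capacity data" that had passed site quality assurance by data cut-off. Missing values were not imputed.
- Precision: "A 2-sided, 95% confidence interval was calculated for change from baseline for each group".
- Interpretation of the Udenafil-Udenafil change, in Statistical methods and again in Efficacy Results: "This change represents persistence of initial effectiveness beyond 26 weeks".
- Results lead-in: "In the Udenafil-Udenafil group, mean exercise capacity was improved while myocardial performance did not deteriorate between 26 weeks and 78 weeks".
- Conclusion: "Improvement in exercise capacity was observed in those who were previously" naïve to the drug, and "there was persistence of effect on exercise capacity for those who were previously treated with udenafil".

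The synopsis gives no margin, retention fraction or threshold for persistence.

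**The concern.** Persistence is a comparison: treated subjects at Week 78 against what they would have been without treatment. Every extension subject took udenafil, so that comparator does not exist. Calling the change itself persistence means that any result, including a fall, would carry the label. The conclusion then reports persistence as a finding, with nothing to judge it against.

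A reader will take away that benefit lasts to 78 weeks. FUEL shows why a within-group rise cannot carry that message. Peak work rate rose by 2.99 W on udenafil and 2.45 W on placebo, with an adjusted difference of 0.19 W (p=0.891; Section 11.4.1.4.2, Table 18). The extension lists a rise of the same 2.99 W in the Udenafil-Udenafil group as part of improved exercise capacity.

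**Working it through.** **Consistency of the stated figures.** The synopsis gives no efficacy n or SD, so the intervals cannot be rebuilt. Their midpoints agree with the means. For "at VAT of 6.57 mL/min (95% CI: -47.9 to 61.0 mL/min", (-47.9 + 61.0)/2 = 6.55. For "Mean increase in work rate at VAT of 0.26 watts (95% CI: -5.1 to 5.6 watts", (-5.1 + 5.6)/2 = 0.25. For VE/VCO2 at VAT (-0.66; -1.6 to 0.3), (-1.6 + 0.3)/2 = -0.65.

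**Assumption.** Let u be the untreated 52-week change. It is not observed. I take u = 0, or u = 2 × the FUEL 26-week placebo change (linear continuation). Neither is a proven bound.

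**Formulas.** D is the FUEL least squares mean difference, at its point estimate.

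- Full retention predicts a Udenafil-Udenafil change of u.
- Full loss predicts u - D.
- Largest loss not excluded = (u - unfavourable CI limit)/D.

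**FUEL inputs.** D and the placebo change come from Tables 12, 13, 15 and 17. The extension used paired data without imputation, so the closest FUEL match for VO2 at VAT is the observed-case (OC) row of Table 12. For the other measures the supplied text gives effect sizes only under LOCF.

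| Measure | D | Placebo change | u | Full loss (u - D) | Extension 95% CI | Largest loss not excluded |
|---|---|---|---|---|---|---|
| VO2 at VAT, mL/min, OC | 50.56 | -8.95 | 0 or -17.90 | -50.56 or -68.46 | -47.9 to 61.0 | 47.9/50.56 = 95%; (-17.90 + 47.9)/50.56 = 59% |
| VO2 at VAT, mL/min, LOCF | 41.58 | -8.01 | 0 or -16.02 | -41.58 or -57.60 | -47.9 to 61.0 | 47.9/41.58 = 115%; (-16.02 + 47.9)/41.58 = 77% |
| Work rate at VAT, W, LOCF | 3.20 | 0.31 | 0 or 0.62 | -3.20 or -2.58 | -5.1 to 5.6 | 5.1/3.20 = 159%; 5.72/3.20 = 179% |
| VE/VCO2 at VAT, LOCF (lower is better) | -0.82 | -0.05 | 0 or -0.10 | 0.82 or 0.72 | -1.6 to 0.3 | 0.3/0.82 = 37%; 0.4/0.82 = 49% |

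Full retention (a change of u) lies inside the interval in every row of this table.

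**Weight-standardised VO2 (mL/kg/min, LOCF effects).**

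- Peak: D = 0.64, placebo -0.89, extension -1.45 (-2.3 to -0.6). With u = 0, full retention (0) is outside the CI and full loss (-0.64) is inside. With u = -1.78, full retention (-1.78) is inside and full loss (-1.78 - 0.64 = -2.42) is outside.
- VAT: D = 0.78, placebo -0.68, extension -1.25 (-2.1 to -0.4). With u = 0, full retention (0) is outside and full loss (-0.78) is inside. With u = -1.36, full retention (-1.36) is inside and full loss (-1.36 - 0.78 = -2.14) sits at the edge of the CI.

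The remaining effect is D + (observed change - u):

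- Peak: 0.64 - 1.45 = -0.81, or 0.64 - 1.45 + 1.78 = +0.97.
- VAT: 0.78 - 1.25 = -0.47, or 0.78 - 1.25 + 1.36 = +0.89.

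The answer runs from effect gone to effect larger than at Week 26. Only u differs between the two ends.

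**The case against.** Within-group description suits an extension whose objectives are safety and pharmacodynamics, so no analysis choice is at fault. That stands: the problem is the inference drawn. The synopsis also reports the weight-standardised falls with intervals for both groups. That stands too, but its conclusion leaves them out.

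It can be argued that decline is expected after Fontan palliation, so stability is itself a benefit. Section 9.5.2 cites a decline of up to 2.6% per year, in a discussion of percent-predicted values. The synopsis neither uses that rate as a comparator nor reports percent predicted, and an external rate is an assumption, not a control.

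Three stronger readings are tempting and are not supported:

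- **The effect was lost.** The weight-standardised falls exceed the FUEL effects, but FUEL placebo subjects also fell, and Section 9.8.2.3 notes that weight gain lowers these values.
- **The VO2-at-VAT interval allows loss of the whole effect.** This is so only against the LOCF effect with zero untreated change. Against the better-matched observed-case effect, full loss (-50.56) falls just outside the limit of -47.9. It is also outside under linear decline on either basis.
- **Results were withheld.** The synopsis gives no efficacy n, no intervals for the peak changes in mL/min, watts and L/min, and no result for VE/VCO2 at peak. The extension report body may contain them, and a persistence criterion may exist in the extension SAP. A criterion would still not supply the missing control.

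**Conclusion.** The persistence claim exceeds the design and should be reworded. The extension neither shows nor refutes persistence of effect to 78 weeks.

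On the stated assumption about untreated change, the VAT measures differ in what they rule out. VE/VCO2 is the most favourable and work rate the least informative; VO2 in mL/min leaves at least 59% loss open. The weight-standardised results change their meaning with the assumed untreated change. These percentages illustrate dependence on that assumption and are not estimates of loss. They also take the FUEL effects as exact, although the observed-case VO2-at-VAT effect has a 95% CI of about 50.56 ± 1.96 × 20.074 = 11.2 to 89.9 mL/min.

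The statement about naïve subjects is literally true for the unstandardised means and for VE/VCO2 at VAT (-0.77; -1.4 to -0.2). It is equally uncontrolled, and it omits that group's weight-standardised falls: -0.93 mL/kg/min at peak (-1.7 to -0.2) and -0.93 at VAT (-1.5 to -0.4).

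**What to change.** In the Section 2 synopsis:

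1. Delete "This change represents persistence of initial effectiveness beyond 26 weeks" in both Statistical methods and Efficacy Results.
2. In Efficacy Results, replace the claim of improved exercise capacity in the Udenafil-Udenafil group with a neutral description of change.
3. Replace the efficacy sentence of the Conclusion with:

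> *At Week 52 mean VO2 (mL/min) and work rate were numerically higher in both groups; weight-standardised VO2 was lower in both groups at peak and at VAT, with CIs excluding zero; VE/VCO2 at VAT was lower in both groups, with a CI excluding zero only in the naïve group. Without a control group these changes cannot be attributed to udenafil, and persistence of effect could not be assessed.*

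The cost is a less favourable claim. No new data or analyses are needed: every statement in the replacement rests on figures already in the synopsis.

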RHI	reactive hyperemia index (ie, the PAT index)
SAE	serious adverse event
SAP	statistical analysis plan
TEAE	treatment-emergent adverse event
VAT	ventilatory anaerobic threshold
VE/VCO ₂	ventilatory equivalents of carbon dioxide
VO ₂	minute oxygen consumption

Note: Abbreviations used only in a table or figure are defined with the table or figure.

5 **Ethics**

5.1 Independent Ethics Committee or Institutional Review Board

An Institutional Review Board (IRB) or Research Ethics Board (REB) reviewed and approved the protocol and the informed consent form (ICF)/assent forms for each of the investigational sites prior to the first dose administration. The first informed consent was signed on 27 July 2016, and the last Week 26 visit was conducted on 27 December 2018.

A copy of the final protocol (Protocol PHN-Udenafil-02, dated 31 August 2017) is provided in [Appendix 16.1.1](#) and a sample electronic case report form (eCRF) is provided in [Appendix 16.1.2](#). The name, address, and chairperson of each IRB/REB, and dates of IRB/REB approval for the protocol and ICF/assent forms are provided in [Appendix 16.1.3](#).

5.2 Ethical Conduct of the Study

This study was conducted in accordance with the International Council for Harmonisation, Harmonised Tripartite Guideline for Good Clinical Practice, 1997; the United States Title 21 Code of Federal Regulations Parts 50, 56, and 312; and the ethical principles that have their origin in the Declaration of Helsinki.

5.3 Subject Information and Consent

Subjects were approached for participation, either in person or by telephone, by study coordinators or Investigators, who obtained assent and/or consent following standard Pediatric Heart Network (PHN) procedures. The specific consent/assent procedures were in compliance with the requirements of each site's IRB/REB. Prior to the performance of any study-related procedures, the subject or subject's parent/legal guardian signed and dated an ICF. Subjects younger than 18 years of age (or as required by state law) signed an assent form. The consent process involved separate consent forms and signatures indicating consent for participation in the udenafil study and consent to submit a blood sample to the genetic biorepository. Sample ICF and assent forms are provided in [Appendix 16.1.3](#).

Each subject was assigned a subject identification number. All interview and clinical research data were stripped of identifiers and labeled with the subject identification number. The enrollment log with participant identifiers was maintained at each site in a secured, locked location available only to the study staff. Samples for DNA were stripped of the subject identification number at the laboratory and assigned distinct specimen numbers without other identifying information.

6 Investigators and Study Administrative Structure

The study was conducted at 30 study centers in North America and the Republic of Korea. Only Investigators qualified by training and experience were selected as appropriate experts to investigate the study drug. At each study site, the Principal Investigator at that site was responsible for study activities. A list of Investigators and their curricula vitae are provided in [Appendix 16.1.4](#). Roles and qualifications of other staff whose participation materially affected the conduct of the study, including the author(s) of the clinical study report and the responsible biostatistician(s), are also listed in [Appendix 16.1.4](#). The Sponsors' approval of this clinical study report is located in [Appendix 16.1.5](#).

Vascular Core Laboratory:	Cincinnati Children's Hospital Medical Center [name]
Biomarker Analysis Laboratory:	Cincinnati Children's Hospital Medical Center [name]
Medical Writing:	MMGL Molecular Genetics Laboratory University of Michigan, [name]
	WebbWrites, LLC [name]

7 **Introduction**

The overall aim of the **Fontan Udenafil Exercise Longitudinal Assessment (FUEL)** trial was to evaluate the efficacy and safety of udenafil as a therapeutic option for those born with single ventricle heart disease who have undergone Fontan palliation. This study was conducted in coordination with the PHN, a consortium of congenital heart centers under the leadership of the NHLBI. At present, medical therapy for these patients is extrapolated from experience with adult-onset systolic heart failure, a condition distinct from the heart failure state associated with the Fontan circulation. The development of a medication specific to the physiology following Fontan palliation would represent a major therapeutic advancement in the field, as there are currently no approved pharmacotherapies for this unique cohort of patients.

The Fontan operation is a palliative procedure for children born with a rare group of congenital heart defects characterized by a single functional ventricle ([Fontan 1971](#); [Kreutzer 1973](#)). This operation, which creates a total cavopulmonary connection, separates the systemic and pulmonary circulations, and reduces the hypoxemia and ventricular volume overload characteristic of single ventricle heart disease. After the Fontan, the single cardiac ventricle is surgically assigned to pump blood only to the systemic circulation. Flow through the pulmonary circulation, now without the assistance of a pumping chamber, is dependent on the gradient between central venous pressure (CVP) and atrial pressure, and on the maintenance of low pulmonary vascular resistance (PVR). The introduction of the Fontan operation has significantly improved the morbidity and mortality burden of single ventricle heart disease through childhood, but has also created a unique population with a substantial need for ongoing cardiac care and intervention, and a limited life expectancy. Although the Fontan operation is initially well tolerated, the unique characteristics of the total cavopulmonary connection lead to progressive cardiovascular dysfunction over time.

Exercise performance is a key metric of cardiovascular health for a variety of congenital and acquired forms of heart disease. For those who have undergone Fontan palliation, this relationship may hold particular importance ([Diller 2005](#); [Diller 2010](#); [Fernandes 2011](#); [Cunningham 2017](#)). The decline in exercise capacity that typically occurs in the second and third decade after the Fontan is associated with an increase in the need for heart failure medications, an increase in the need for hospitalization, and an increase in the prevalence of both heart transplantation and mortality. The limitations in exercise capacity in the Fontan circulation are related to the absence of a sub-pulmonary ventricle. Without a pumping chamber to help deliver blood through the lungs and back to the heart, the ability to increase cardiac output is dependent on low PVR and an elevation in CVP. In a 2-ventricle circulation,

an increase in right-heart pressure to nearly 50 mmHg is key to reaching the increase in cardiac output of 4-fold or greater seen at peak exercise ([Stickland 2006](#); [Argiento 2010](#)). In a single ventricle circulation, however, CVP cannot reach a pressure near that which can be achieved by a typical right ventricle. In this setting, the ability to augment cardiac output is limited and the role of PVR during exercise is magnified ([Goldberg 2013](#); [Navaratnam 2016](#); [Egbe 2017](#)). By minimizing PVR, one can decongest the venous system at baseline and allow for an improvement in the ability to increase flow through the pulmonary vasculature during exercise ([Gewillig 2010](#); [Goldstein 2010](#); [La Gerche 2010](#)).

Udenafil is a selective, long-acting phosphodiesterase type 5 (PDE-5) inhibitor that has unique characteristics within the class and has demonstrated effectiveness as a pulmonary vasodilator in the treatment of patients with pulmonary hypertension ([Chang SA 2019](#); [Chang H-J 2019](#)). Given the need for a medication specific to those with a total cavopulmonary connection, Mezzion Pharma Co. Ltd, in partnership with the PHN, has developed udenafil as a potential therapeutic option for those who have undergone the Fontan procedure. At present, udenafil is the only pharmacotherapy to have undergone pharmacokinetic (PK) analysis through a Phase 1/2 dose-finding study in this population. This study demonstrated that a dose of 87.5 mg twice daily (BID) provided the highest maximal plasma concentration with an acceptable drug tolerability and a clinical improvement in ventricular performance.

After completion of the Phase 1/2 study, Mezzion Pharma Co. Ltd continued its partnership with the PHN to create and execute the FUEL study. This 400-patient, double-blind, placebo-controlled trial is the largest medication trial ever undertaken for those with any form of congenital heart disease and was conducted to determine the safety and efficacy of daily oral therapy with udenafil in adolescents with single ventricle heart disease who had undergone Fontan palliation. The primary aim was to determine the effect of udenafil on exercise performance over a 26-week treatment period. Safety was evaluated throughout the 26-week period and for up to an additional 3 months. Mezzion Pharma Co. Ltd and the PHN are also conducting an open-label extension trial to continue to evaluate the tolerability and safety of udenafil over an additional 3-year time period.

8 Study Objectives

The primary objective of the study was to evaluate the effect of 26 weeks of treatment with udenafil (87.5 mg, BID) on exercise capacity in adolescents with Fontan physiology.

The secondary objectives of this study of adolescents with Fontan physiology were to:

- Determine the effect of 26 weeks of treatment with udenafil on echocardiographic indices of systolic and diastolic ventricular performance.
- Determine the effect of 26 weeks of treatment with udenafil on endothelial function.
- Evaluate the effect of 26 weeks of treatment with udenafil on serum brain natriuretic peptide (BNP) level, a biomarker of heart failure.
- Evaluate the safety of udenafil when given over a 26-week time period.
- Determine if 26 weeks' treatment with udenafil alters functional health status.
- Establish a collection of genetic material to identify genetic determinants of exercise capacity and response to udenafil and for unspecified future studies.
- Determine the prevalence and severity of complications, including protein-losing enteropathy, plastic bronchitis, hospitalizations, cardiac transplantation and death in adolescents who received udenafil.
- Explore the impact of udenafil on atrial and ventricular premature beats and arrhythmia burden.

9 Investigational Plan

